6.5.5 Non-Research Standard of Care

Not Applicable

7. STUDY INTERVENTION DISCONTINUATION AND SUBJECT DISCONTINUATION/WITHDRAWAL

7.1 Halting Criteria and Discontinuation of Study Intervention

7.1.1 Individual Study Product Halting

Study product administration for any given subject may be stopped for SAEs, clinically significant adverse events, severe laboratory abnormalities, or any other medical conditions that indicate to the Investigator that continued dosing is not in the best interest of the patient.

If signs and symptoms of a clinically significant hypersensitivity reaction occurs during or shortly after an infusion of Remdesivir or administration of the blinded study products (oral and IV push), administration must be stopped and treated as needed. Subjects who have the study

Appendix D - ACTT-4: Baricitinib/Remdesivir vs Dexamethasone/Remdesivir

product stopped for a safety related issues will not continue with dosing. In addition, subjects who have an allergic reaction that is temporally associated with study product administration and the PI believes it to be related to study product will not receive any more study product. See Section 7.1.1.2 below for additional halting criteria for the blinded study products.

In addition, a subject in this clinical study may discontinue study drug at their request for any reason. Every effort should be made to encourage subjects to remain in the study for the duration of their planned outcome assessments. Subjects should be educated on the continued scientific importance of their data, even if they discontinue study drug.

Unless the subject withdraws consent, those who discontinue study drug early will remain in the study. The reason for subject discontinuation of study drug should be documented in the case report form.

7.1.1.1 Remdesivir Halting

See [Section 6.1.4](#). for information about dosing modifications due to laboratory abnormalities.

7.1.1.2 Oral and IV Study Product Halting

See [Section 6.1.4](#). for information about dosing modifications for the blinded oral study product due to laboratory abnormalities. Otherwise, criteria for discontinuing administration of the blinded oral and IV push study products are the same as outlined below.

The subject should not receive any additional blinded oral and IV push study product if they develop any of the following conditions during the study:

- VTE (DVT/PE).
- Suspected drug-induced liver injury with the appearance of fatigue, nausea, vomiting, right upper-quadrant pain or tenderness, fever, rash, and/or eosinophilia (>5%).
- New malignancy (except for successfully treated basal or squamous cell skin carcinoma).
- A systemic fungal infection is confirmed.
- Clinically significant hypersensitivity, including anaphylaxis or anaphylactoid reaction during administration of either blinded oral or IV study product

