Appendix D - ACTT-4: Baricitinib/Remdesivir vs Dexamethasone/Remdesivir

Any dose that is held as described above, may be given later that day if the laboratory parameters improve. Any daily dose that is missed during the study due to any reason is not made up. The treatment course continues as described above even if the subject becomes PCR negative while hospitalized. If oral study product is held for more than 2 days, consider that the subject may not be receiving any anti-inflammatory. If the clinical condition requires, an open-label (off-study) dexamethasone or other anti-inflammatory agent may be added while the oral study product is held. No protocol deviation for prohibitory medications (i.e., off-study dexamethasone) would be required for these days of anti-inflammatory coverage while the subject has oral study product held.

For laboratory values that meet permanent discontinuation thresholds (see [Section 7.1](#)), study product should be discontinued. However, if in the opinion of the investigator, the laboratory abnormality is due to intercurrent illness or another identified factor, laboratory tests may be repeated once.

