6.3.2.3 Unblinding for adverse event

If a Serious Adverse Event occurs, that is thought to be related to the study drug, and the treating clinician believes that knowledge of the treatment arm may change the therapy provided to the patient, the individual subject can be unblinded. If unblinded for SAE, the investigator may decide to have the blinded study product and/or remdesivir infusions discontinued based on the adverse event that led to unblinding and the benefit-risk analysis. The subject should remain on study through the Day 60 visit. The procedure for emergency unblinding will be further detailed in the Manual of Operations.

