6.5.2 Prohibited Concomitant Therapy

As the study is comparing baricitinib to dexamethasone, additional baricitinib, dexamethasone and other glucocorticoids are prohibited unless the subject worsens and requires invasive mechanical ventilation (see Section 6.5.4). In addition, if oral study product is held for more than two days and the clinical condition requires, an open-label (off-study) dexamethasone or other anti-inflammatory agent may be added while the oral study product is held (Section 6.1.4). Exceptions to the steroid prohibition include: mineralocorticoids for standard indications are permitted (e.g., adrenal insufficiency, shock) and low-dose prednisone as part of immunosuppression regimen for solid organ-transplant patients is allowed (e.g., prednisone 5 mg po daily).

Strong inhibitors of organic anion transporter 3 (OAT3) such as probenecid are prohibited during the study.

Concomitant use of any other experimental treatment or off-label use of marketed medications intended as specific treatment for COVID-19 or SARS-CoV-2 infection, and not specified in the local or NIH COVID-19 Treatment Guidelines are prohibited. Specifically, use of any biologic therapy not specified on the written policy or guideline are prohibited including: monoclonal antibodies targeting cytokines (e.g., TNF inhibitors; interleukin-1[IL-1], IL-6 [tocilizumab or sarilumab]), or T-cells (e.g., abatacept); monoclonal antibodies targeting B-cells (e.g., rituximab, and including any targeting multiple cell lines including B-cells); JAK inhibitor(s) (e.g., baricitinib, imatinib, gefitinib, acalabrutinib, tofasitinib); and any type of interferon, convalescent plasma, or immunoglobulin (IgG) therapies for COVID-19. Similarly, the concomitant use of hydroxychloroquine to treat COVID-19 is prohibited unless it is included in the local institutional treatment guidelines (and even then, it is discouraged given the interaction with remdesivir).

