In ACTT-4, non-study product (off-study) baricitinib, dexamethasone and other glucocorticoids are prohibited unless the subject worsens to require invasive mechanical ventilation (ordinal score 7). Mineralocorticoids for standard indications are permitted (e.g., adrenal insufficiency, shock). Low-dose prednisone as part of immunosuppression regimen for solid organ-transplant patients is allowed as part of standard of care (e.g., prednisone 5 mg po daily).

If additional (off-study) baricitinib, dexamethasone or another glucocorticoid is given when a subject is not an ordinal scale category 7, the investigator should file a protocol deviation for use of the prohibited medication and decide whether the blinded study products should be discontinued. The subject should remain on study and continue with the SOA as described in the protocol though the Day 60 visit. An exception to this is when oral study product is held for more than 2 days and the clinical condition requires that an open-label (off-study) dexamethasone or other anti-inflammatory agent be added while the oral study product is held (see Section 6.1.4).

- The preference is to continue study medication as originally assigned (i.e. continue blinded baricitinib or placebo and continue blinded dexamethasone or placebo) as well as the remdesivir infusions. The subject should remain on study though the Day 60 visit.
- Recognizing the treating clinician may request to stop the randomized blinded study medication, the next preferred option is that the baricitinib/placebo po component and the dexamethasone/placebo IV component are discontinued without unblinding. This will allow the treating clinician to pick any regimen needed for the subject. In this scenario, remdesivir infusions should continue and the subject should remain on study though the Day 60 visit.
- If the treating clinician needs to know prior treatment, the site investigator can request that the subject treatment assignment be unblinded. This is the least preferred option as it unblinds treatment assignment. However, it is available to ensure clinicians have information available to give their patients optimal care. In this scenario, remdesivir infusions should continue and the subject should remain on study through the Day 60 visit.

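### ACTT-4: after both blinded products are permanently stopped, off-study steroid before ventilation is still, read literally, a prohibited medication, because the exception names only a held oral product

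*Protocol*

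**What the plan says.** All references are to Appendix D of the Protocol.

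- **Permanent stop.** Section 7.1.1.2 lists VTE, suspected drug-induced liver injury, new malignancy, confirmed systemic fungal infection and clinically significant hypersensitivity. After any of these, "The subject should not receive any additional blinded oral and IV push study product". Section 7.1.1 keeps subjects who stop study drug in the study unless they withdraw consent.
- **Prohibition.** Section 6.5.2 states that, beyond study product, baricitinib, "dexamethasone and other glucocorticoids are prohibited unless the subject worsens and requires invasive mechanical ventilation". For use outside ordinal category 7, Section 6.5.4 says "the investigator should file a protocol deviation for use of the prohibited medication".
- **Exception.** Section 6.1.4 asks sites, once the oral product has been held for more than two days, to "consider that the subject may not be receiving any anti-inflammatory". If the clinical condition requires, off-study "dexamethasone or other anti-inflammatory agent may be added while the oral study product is held", and no deviation is needed for those days. Section 6.5.2 repeats this, and 6.5.4 words it as "An exception to this is when oral study product is held for more than 2 days".
- **Other steroid exceptions.** Section 6.5.2 also allows mineralocorticoids for standard indications and low-dose prednisone in organ-transplant recipients. Neither is COVID-19 treatment.

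**The concern.** The exception exists so that a subject is not left without anti-inflammatory cover. A permanent stop under 7.1.1.2 leaves every subject in that position, yet all three statements of the exception name only a hold.

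Subjects enter on oxygen (ordinal 5 or 6). Section 2.2.4.2 says dexamethasone likely improves outcome in hospitalized patients. Section 2.1.1 cites 28-day mortality of 23.3% against 26.2% in the RECOVERY patients on oxygen without invasive ventilation. A site that follows the letter after a permanent stop gives no glucocorticoid until the subject is ventilated, which is already a primary-endpoint event. A site that treats earlier files a prohibited-medication deviation. A third site may read held broadly and file nothing.

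**Working it through.** No plan figure has to be reproduced, because the point rests on the wording. The steps are as follows.

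**1. Does the prohibition still apply after a permanent stop?** Yes. The subject remains in the study (7.1.1). Neither 6.5.2 nor 6.5.4 ties the prohibition to still receiving blinded product.

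**2. Does the exception name this case?** No. Section 6.1.4 describes temporary interruptions of the oral product, most with stated resume criteria. It refers separately to permanent discontinuation thresholds and sends the reader to Section 7.1 for those.

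**3. Whom does the exception's reason fit?** Section 6.1.2 runs the IV product to Day 10 and the oral product to Day 14. For a hospitalized, non-ventilated subject:

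| Situation | Baricitinib arm: active study anti-inflammatory | Dexamethasone arm: active study anti-inflammatory | Named in exception? |
|---|---|---|---|
| Oral hold of more than 2 days, through Day 10 | None | Dexamethasone continues | Yes |
| Oral hold of more than 2 days, Days 11 to 14 | None | None (IV course over) | Yes |
| Permanent stop under 7.1.1.2 | None | None | No |

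Through Day 10 the reason applies during a hold only to the baricitinib arm. After a permanent stop it applies to both arms.

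**4. Does another provision close the gap?**
- Section 6.3.2.3 allows unblinding for a related serious adverse event if "knowledge of the treatment arm may change the therapy provided to the patient", but does not lift the prohibition.
- Section 6.5.4 lets the clinician choose any regimen once both products are stopped, but only for subjects who have progressed to ventilation.
- Section 6.5.2 prohibits other experimental or off-label COVID-19 treatments that are "not specified in the local or NIH COVID-19 Treatment Guidelines are prohibited". Guideline-listed agents other than baricitinib and glucocorticoids therefore remain available, and the gap is confined to those two.

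**5. How many subjects?** VTE is the only trigger with a usable rate in the documents. Section 2.2.3.1 gives 21 and 16 subjects with VTE in ACTT-2, and its Table 4 gives denominators of 507 and 509: (21 + 16)/(507 + 509) = 37/1016 = 3.6%. This is an upper guide for that trigger. Only VTEs during dosing in non-ventilated inpatients matter here, and that share is not given. ACTT-2 also included subjects ventilated at baseline, (54 + 57)/(515 + 518) = 111/1033 = 10.7% (Section 2.1.1, Table 2), whom ACTT-4 excludes. No comparable rate is given for the other four triggers.

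**The case against.** **The reading is contestable.** Held is not defined. Section 6.1.4 also instructs sites to hold the oral product in subjects on dialysis, with no resume criterion for dialysis, so a hold need not be short. A product stopped for good has also not been given for more than two days. In addition, 6.5.4 tells the investigator filing a deviation to decide whether to discontinue the blinded products, which is moot once both are stopped; that rule was evidently written with subjects still on treatment in mind. This stands as far as it goes: the text is ambiguous and not self-contradictory. But 6.1.4 does treat permanent discontinuation as a separate matter, so the literal reading is reasonable and sites may divide.

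**A wider exception invites crossover.** Section 7.1.1 lets an investigator stop study product on judgement, or a subject stop on request. If the exception covered those stops, a site could stop both products, give open-label dexamethasone and report no deviation, and in the baricitinib arm that is crossover to the comparator. This objection stands, and the remedy must be confined to the conditions listed in 7.1.1.2.

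**The halting rule stops dexamethasone on purpose.** The amendment history (Section 10.4, version 10.0) records that the oral and IV halting rules were combined on regulatory advice. Relief should therefore depend on the stopping reason not contraindicating a steroid. A blanket permission would go too far.

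**It is only a deviation form.** Largely true. A reader might infer that the protocol bars treatment or abandons these subjects. It does neither: follow-up continues, guideline-listed alternatives remain, and treating means reporting a deviation.

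**Conclusion.** The point holds as a wording gap of low severity with a patient-safety side. Read literally, ACTT-4 labels glucocorticoid for COVID-19 a prohibited medication in non-ventilated subjects whose two blinded products were permanently stopped under 7.1.1.2, although the exception's own reason fits all of them. This assumes that held excludes a permanent stop. The Manual of Procedures, which is not available here, might say otherwise.

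Two stronger inferences are not supported. The first is that the primary analysis or power is compromised. The analysis is by intention to treat in all randomized subjects (9.3), and the power figures in Table 9 of Section 9.2 use no input on concomitant treatment. The second is that 3.6% of the planned 1500, or 0.0364 × 1500 = about 55 subjects, would be affected. That count takes every VTE, whether or not it occurred during dosing in a non-ventilated inpatient, and ignores the other triggers. The documents support only the statement that the number is small and cannot be fixed.

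**What to change.** In 6.1.4, 6.5.2 and 6.5.4, add to the exception the case where both blinded products have been permanently discontinued for a condition listed in 7.1.1.2. Do not include discretionary or subject-requested stops under 7.1.1.

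In that case allow off-study dexamethasone or an equivalent glucocorticoid, without a deviation, when the clinical condition requires it and the treating clinician judges that the stopping reason does not contraindicate it. Systemic fungal infection and hypersensitivity to the IV product are examples where it would not be given. Do not extend this to off-study baricitinib.

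The cost is a short addition in three sections. Sample size, analysis and data collection stay as they are, since 6.5.3 already records systemic corticosteroids through Day 29, including after discharge. The downside is slightly more off-study steroid in a small number of subjects, including some crossover in the baricitinib arm. The existing exception already accepts such crossover during an oral hold.

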7.1.2 Study Halting

Given the potential severity of COVID-19, there are no pre-specified study stopping rules. Instead there will be close oversight by the protocol team and frequent DSMB reviews of the safety data.

7.2 Withdrawal from the Study

Subjects are free to withdraw from participation in the study at any time upon request, without any consequence. Subjects should be listed as having withdrawn consent only when they no

Appendix D - ACTT-4: Baricitinib/Remdesivir vs Dexamethasone/Remdesivir

longer wish to participate in the study and no longer authorize the Investigators to make efforts to continue to obtain their outcome data or safety assessment.

The investigator may also withdraw a subject from the study. However, the investigator will be encouraged to allow subjects to remain in the study to be followed for safety and final outcome assessment at Days 29 and 60 (i.e., the ordinal scale and mortality) even if they decide to discontinue study products and research laboratory draws. Withdrawing a subject from the study due to an inability to contact them for the Day 15 and/or Day 22 follow-up visit is discouraged given the possibility of readmission and chaotic social circumstances resulting from the pandemic.

Subjects who withdraw from this study or are lost to follow-up after signing the informed consent form (ICF) and administration of the study product, will not be replaced. The reason for subject withdrawal from the study will be recorded on the appropriate CRF.

7.3 Lost to Follow-Up

A subject will be considered lost to follow-up if the site is unable to contact him or her by phone or other means such as text, email, fax or letter (as approved by the IRB) for all follow-up assessments at Day 15, 22 and 29. In lost to follow-up cases, attempts to contact the subject should be made and these efforts should be documented in the subject's records.

7.4 Readmission

If a subject is discharged from the hospital and then readmitted prior to Day 11, they may be given the remainder of the remdesivir infusions, baricitinib/po placebo and dexamethasone/IV placebo component. If prior to Day 15, they may be given the remainder of the baricitinib/po placebo components. If the subject did not withdraw his/her consent to participate in the study, there is no need to reconsent upon readmission to the study hospital. However, the site will need to inform them that since he/she was readmitted, study product administration will resume and confirm that they still agree to receive study product.

The natural history of COVID-19 and its impact on pre-existing medical conditions is not completely understood. Because of this, all readmissions, regardless of reason, should be documented and the subject should get daily clinical status assessments (i.e., ordinal scale) and other procedures done as per the SOA upon readmission. If the subject is re-admitted with diminished mental capacity, the site should discuss continued study participation with a LAR.

The study team will need to notify the study pharmacist of the readmission. The subject will not get the doses that they missed after being discharged. Upon readmission, the subject will get maintenance doses of infusion only since they already received the loading dose of the study product infusion on Day 1. No remdesivir or dexamethasone/IV placebo component study product infusions should be given past Day 10. No baricitinib/po placebo component should be given past Day 14. For all data collection procedures required for those readmitted, please see the MOP.

8. STUDY ASSESSMENTS AND PROCEDURES

8.1 Screening and Efficacy Assessments

8.1.1 Screening Procedures

Post consent screening procedures may be done over one to two calendar days (from Day -1 to Day 1). See Section 5.6.1 for allowable pre-screening procedures. However, in many cases all the screening assessments can be done in less than 24 hours. If that is the case, Day 1 pre-study product administration baseline assessments, specimen collection and the initial study product administration can occur on the same calendar day as the screening procedures.

After the informed consent, the following assessments are performed to determine eligibility:

- Confirm the positive SARS-CoV-2 test result (per inclusion criteria).
- Confirm that patient does not have a positive influenza test during the current illness for which they are being screened and possibly enrolled. Influenza testing is not required per protocol.
- Take a focused medical history, including the following information:
 - Day of onset of COVID-19 signs and symptoms.
 - Prior enrollment in ACTT-3 or ACTT-4.
 - History of vaccinations within 4 weeks before screening and planned vaccinations.
 - Exclusionary vaccine history includes any live vaccine (that is, live attenuated) within 4 weeks before screening, or intend to receive a live vaccine (or live attenuated) during the study. Note: Use of non-live (inactivated) vaccinations is allowed for all subjects including the recently EUA approved COVID-19 vaccines. Pre-study receipt of SARS-CoV-2 vaccine should be documented in the Medical History eCRF.
 - History of chronic medical conditions, including chronic oxygen requirement and/or use of CPAP or BiPAP at home, prior to onset of COVID-19. See conditions included in exclusion criteria and on the Medical History (CMX) data collection form.
 - History of medication allergies.
 - Medications and therapies for this current COVID-19 illness and history of any medication listed in the exclusion criteria. Site should identify if the patient received any dexamethasone in the 7 days prior to randomization.
 - Ask if the patient is participating in another clinical trial or plans to enroll in another clinical trial in the next 28 days.
- Women of childbearing potential should be counseled to either practice abstinence or use at least one primary form of contraception not including hormonal contraception from the time of screening through Day 29. Women should be confirmed to not be breastfeeding.
 - Note: If a woman is either postmenopausal (i.e., has had ≥ 12 months of spontaneous amenorrhea) or surgically sterile (i.e., has had a hysterectomy, bilateral ovariectomy (oophorectomy), or bilateral tubal ligation), she is not considered to be of childbearing potential.

- Blood for screening laboratory evaluations, if not done as part of routine clinical care in the preceding 48 hours, should be collected to evaluate the following parameters:

- White blood cell count (WBC) with differential
 - Assess ANC and ALC as per exclusion criteria
- Serum creatinine (and calculate eGFR)
 - Any automated calculation by the clinical laboratory or published formula for this calculation is acceptable. The site should select a formula to be used for all subjects enrolled at the site for the duration of the study.
- Do urine or serum pregnancy test during screening for women of childbearing potential or site may use test done prior to screening during this current hospital admission as long as patient has been confined in hospital since test was done. See instructions below for women who are less than 6 weeks postpartum:
 - Do not do a pregnancy test if the patient is post-partum and has not left the hospital since delivery. The pregnancy test will likely give a false-positive result as serum human chorionic gonadotropin (hCG) is usually detected for up to 4 to 6 weeks after delivery.
 - For women who are less than 6 weeks postpartum and have left the hospital, any positive pregnancy test should be repeated to determine if the HCG is declining as predicted after delivery and therefore the result is a false-positive. Of note, women who are less than 6 weeks postpartum and had heterosexual intercourse since delivery and hospital discharge are unlikely to be pregnant because the average time to first ovulation varies from 45 to 94 days postpartum, with the earliest reported ovulations at 25 and 27 days postpartum.

Clinical screening laboratory evaluations will be performed locally by the site laboratory. The volume of venous blood to be collected is presented in [Table 7](#). A screening lab (i.e., from the hematology and chemistry laboratory panels) may be repeated once if, in the opinion of the investigator, the laboratory abnormality is due to an intercurrent transient condition or it is an aberrant laboratory value.

The overall eligibility of the subject to participate in the study will be assessed once all screening values are available. The screening process can be suspended prior to complete assessment at any time if exclusions are identified by the study team.

Study subjects who qualify will be randomized in the Advantage eClinical system, and all others will be registered as screen failures. The ordinal scale should be done at the time of randomization; the site will need this data to randomize the subject in eClinical. The study team has 24 hours to complete other Day 1 baseline assessments prior to the first study product administration including the collection of the OP swab and blood and completing or recording a baseline physical examination that was done, including weight and height (height can be self reported). Clinical laboratory tests collected as part of routine care of the patients in the 36 hours prior to first dose qualify for baseline safety tests on Day 1.

If a subject is found to be ineligible AFTER being randomized and they did not receive any study product, the site should file an early study termination and stop all study procedures including specimen collection.

If the subject is found to be ineligible AFTER being randomized and did receive study product, they may continue on study if the PI has no safety concerns with their continued participation. The site should file a study protocol deviation (i.e., checkbox: met exclusion criteria). However, if the PI feels that the risk of participation outweighs the benefit, the site should file an early study termination.

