9.3 Populations for Analyses

Appendix D - ACTT-4: Baricitinib/Remdesivir vs Dexamethasone/Remdesivir

The primary analysis will be based on an intention-to-treat population, including all subjects randomized. Safety analyses will be based a modified intent-to-treat population consisting of all subjects who received at least one dose of any investigational product.

An Endpoint Review Committee consisting of the DMID MO, her designees and the blinded statistical team may review endpoints, medications, deviations, and other special cases where expert opinion is requested for handling complicated cases.

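### ACTT-4 section 8.1.1 ends study follow-up, not just product, for randomized subjects later found ineligible, leaving avoidable gaps in Day 29 outcomes

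*Protocol*

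**What the plan says.** Protocol Appendix D, section 8.1.1 (Screening Procedures), covers subjects found ineligible after randomization.

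- **Dosed.** Such subjects "they may continue on study if the PI has no safety concerns with their continued participation". Otherwise, "if the PI feels that the risk of participation outweighs the benefit, the site should file an early study termination".
- **Not dosed.** Here "the site should file an early study termination and stop all study procedures including specimen collection", with no judgement left to the site.

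Other sections of the same appendix set the follow-up and analysis rules.

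- **Section 7.1.1:** "Unless the subject withdraws consent, those who discontinue study drug early will remain in the study".
- **Section 7.2:** "The investigator may also withdraw a subject from the study", but "the investigator will be encouraged to allow subjects to remain in the study to be followed for safety and final outcome assessment". The encouragement extends to both the Day 29 and the Day 60 visit, even after product and research blood draws have stopped.
- **Section 9.3:** "The primary analysis will be based on an intention-to-treat population, including all subjects randomized". The safety set consists of "subjects who received at least one dose of any investigational product".
- **Section 9.4.2:** the primary test compares Kaplan-Meier estimates of 28-day ventilation-free survival, with Greenwood's variance.

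**The concern.** Section 8.1.1 treats two decisions as one: whether a subject should go on receiving product, and whether the subject should still be observed. For a dosed subject the alternative to continuing is termination of participation. Exclusion criterion 1 in section 5.2, which refers to people whose ACTT participation was terminated early, supports reading termination as the end of participation rather than of dosing alone.

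An analysis of all randomized subjects needs outcomes on all of them. A subject terminated in the first days would most naturally be censored in the Kaplan-Meier estimate. That treats the subject's later risk of ventilation or death as equal to that of subjects who stayed. For dosed subjects the trigger is a judgement of risk made after randomization, so that equality is open to doubt. Mortality and adverse-event data on dosed subjects are exposed to the same loss.

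**Working it through.** **1. Comparison with the rest of Appendix D.** In other awkward situations the appendix keeps the subject under observation.

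| Section | Situation | Instruction |
|---|---|---|
| 5.4 | Co-enrolled in a prohibited trial | Record a deviation, do not withdraw, follow in full |
| 5.6.2 | Terminal illness, hospice | Encourage staying for Day 29 by chart or phone |
| 6.3.2.3 | Unblinded for a serious adverse event | Stay on study to Day 60 |
| 6.5.4 | Prohibited off-study anti-inflammatory | Record a deviation, stay on study to Day 60 |
| 7.1.1 | Product stopped early | Stay unless consent is withdrawn |
| 8.1.1 | Found ineligible after randomization | Terminate (at the investigator's judgement if dosed, always if not dosed) |

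Section 8.1.1 is the exception. Its direct conflict is with 7.1.1, because an investigator's risk judgement is not a withdrawal of consent.

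**2. The plan's own sample size.** Inputs from section 9.2: 0.85 versus 0.90, two-sided 5%, 80% power, 8% loss. With unpooled variance, n per arm = (1.960 + 0.842)² × (0.85×0.15 + 0.90×0.10) / 0.05² = 683, or 1366 in total. The pooled version gives 686 per arm, or 1372. Both are close to the stated 1382, which comes from an exact test. At 691 per arm the power is 80.3% (pooled) or 80.5% (unpooled), against the stated 80% and 80.5%. 1382 / 0.92 = 1502.2, which agrees with about 1500. The plan's figures reproduce, and this point disputes none of them.

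**3. Effect on power.** Assume terminations come on top of the 8% loss, with 1500 enrolled.

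| Total loss | Evaluable | Power (pooled) |
|---|---|---|
| 8% | 1380 | 80.3% |
| 9% | 1365 | 79.8% |
| 10% | 1350 | 79.4% |
| 12% | 1320 | 78.5% |

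**4. Effect on one arm's estimate.** The protocol gives no rate of ineligibility found after randomization, so the inputs here are assumptions. Let q be the arm's true event probability, f the share terminated before any event, and r their risk relative to retained subjects, whose risk is q′. Then q = q′(1 − f) + f·r·q′, so q′ = q / (1 + f(r − 1)). Kaplan-Meier estimates 1 − q′, and event-free survival is overstated by q − q′. With q = 0.15:

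| f | r = 1.5 | r = 2 | r = 3 |
|---|---|---|---|
| 1% | 0.07 | 0.15 | 0.29 |
| 2% | 0.15 | 0.29 | 0.58 |
| 3% | 0.22 | 0.44 | 0.85 |
| 5% | 0.37 | 0.71 | 1.36 |

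Entries are percentage points. For example, f = 5% and r = 3 give q′ = 0.15/1.10 = 0.1364, a bias of 1.36 points.

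**5. Effect on the comparison.** Take no true difference, q = 0.125 in both arms, 750 per arm, and r = 3 in both.

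- 2% versus 2%: spurious difference 0, type I error 5.0%.
- 3% versus 1%: 0.125/1.02 − 0.125/1.06 = 0.46 points. With a standard error of 1.70 points the type I error is about 5.9%.
- 5% versus 1%: 0.125/1.02 − 0.125/1.10 = 0.89 points. With a standard error of 1.69 points the type I error is about 8.2%.

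**The case against.** The strongest reply is that section 7.2 already allows investigator withdrawal and already encourages follow-up to Days 29 and 60. On that view 8.1.1 is a specific rule for a small group sitting beside a general one, and only a cross-reference is missing. This is partly right. The conflict with 7.2 is one of emphasis, since 7.2 permits what 8.1.1 instructs. It does not remove the conflict with 7.1.1. Nor does a site following 8.1.1 as written find any prompt to keep collecting outcomes.

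Several stronger readings are tempting, and the document does not support them.

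- **That the intention-to-treat population is contradicted.** A reader might infer this from 9.3. But 9.3 defines who is analysed, and terminated subjects remain in that set. Completeness of outcome data is what suffers.
- **That the loss is necessarily informative.** Section 8.1.1 turns on the risk of participation, not on prognosis for ventilation or death. Some exclusions (prior ACTT enrollment, drug allergy, probenecid, live vaccine) have no evident link to prognosis. Others, such as low eGFR or lymphopenia, may have one. Informative loss is plausible but not shown. Treatment is normally blinded when the decision is made, which limits imbalance between arms.
- **That the estimate could move by more than the 5-point design difference.** A reader might assume that 3% of 1500 (45 subjects) are terminated, place all of them in one arm of 750, and read 45/750 as a 6-point shift. That needs an unsourced rate, complete imbalance under blinding, and an event in every one of them. Even then, early censoring moves the estimate by f times retained survival, which is 0.06 × 0.85 to 0.06 × 0.90, or 5.1-5.4 points.
- **That safety follow-up of dosed subjects stops entirely.** The instruction to stop all procedures appears only in the sentence on undosed subjects, and section 8.3.2 still requires serious adverse events to be followed to resolution or stabilization.

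Section 9.4.3 leaves missing data, including informative censoring, to the SAP, which is not at hand. The censoring of these subjects is therefore an inference. A SAP rule can still only model outcomes that were never collected.

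**Conclusion.** The point stands as an internal inconsistency with a cheap remedy. Section 8.1.1 conflicts with 7.1.1, runs against the retention aims of 7.2 and 5.6.2, and creates avoidable missing Day 29 outcomes in a primary analysis of all randomized subjects. The mandatory termination of undosed subjects raises the same problem.

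The likely size is small. Under assumed ranges (1-5% of an arm terminated early, 1.5-3 times the retained risk, 15% event rate) the overstatement is about 0.1-1.4 percentage points per arm. Power falls to no lower than 78.5% at 12% total loss. With the same excess risk in both arms, type I error stays at 5% when terminations are equal and reaches about 8% only in the most unequal case tried. These sizes rest on the assumptions above, because the protocol gives no frequency.

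**What to change.** Reconcile section 8.1.1 with 7.1.1, 7.2 and 9.3 by separating the end of study product from the end of follow-up.

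- For every randomized subject later found ineligible, dosed or not, keep collecting ordinal scale or ventilation status and mortality through Day 29 and Day 60, by chart or phone, unless consent is withdrawn.
- For dosed subjects, also collect serious adverse events through Day 29, as section 8.3.5 already requires.
- Align the investigator-withdrawal wording in 7.2, so that the new text does not create a fresh conflict.
- State the day count for undosed subjects, for example from randomization, because section 6.1.2 defines Day 1 by first product.

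Whether product continues is a clinical matter and is not addressed here. No planned number changes. The cost is a few sentences, a note to sites, and a small number of extra chart or phone follow-ups, by methods the protocol already allows in sections 5.6.2 and 8.1.3.
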